#### **Epidemiology:**

Data on incidence of PCOS is hugely influenced by the definition of PCOS followed in the respective study. PCOS incidence has been reported to vary from 2.2-26% worldwide (1-5). In India, only a handful of epidemiological studies have been reported on PCOS. The following table summarizes results of those studies. Table 1: Summary of Epidemiological Studies on PCOS in India

 Study Design	Location	Sample size	Age range	Incidence (%)	PCOS definition	Non- obese PCOS (%)	Reference
Cross- sectional	Mumbai	778	15-24	22.5 10.7	Rotterdam NIH	71.8%	Joshi B et al Indian Journal of Endocrinology and Metabolism / May-Jun

							2014 / Vol 18   Issue 3
Cross- sectional	Kanchipuram/Chennai	1068	18-24	6	Rotterdam	62%	Bharathi, RV Middle East Fertility Society Journal 22 (2017) 313– 316
Cross- sectional	Bangalore	460	18-45	9.13	Rotterdam	-	R Nidhi et al J Pediatr Adolesc Gynecol 24 (2011) 223e227
Cross- sectional	Dehradun	170	16- 30+	41	NIH	14%	Choudhary A et al. Int J Reprod Contracept Obstet Gynecol. 2017 Nov;6(11):4971-4975
Cross- sectional	Bhopal	500	17-24	8.4	Rotterdam	17%	Gupta M et al. Int J Community Med Public Health. 2018 Jan;5(1):95-100
Cross- sectional	Sevagram	200	15-34	50	Rotterdam	-	Chhabra S J Obstet Gynaecol. 2010 Jan;30(1):41-5.
Cross- sectional	Vellore	126	12-19	18	Rotterdam	-	Balaji, S et al Biomed Res Int. 2015;2015:158951.

As can be seen in the table, PCOS incidence varied widely from 6-50% among different studies. This calls for multi-centre studies involving larger sample size and uniform diagnostic criteria. Few studies (Bharathi, RV et al and Balaji S et al) have indicated higher incidence of PCOS in urban women. While stress and other life-style

related factors may contribute to a higher abundance as suggested in these articles, underreporting in rural set up due to stigma involved with consequences of PCOS may also contribute to this difference. One of the striking features of PCOS in India is that a significant percentage of PCOS patients are non-obese at diagnosis. However, it should be noted that all these studies stratify subjects based on BMI and/or waist circumference. None of them analyzed the total body fat using technologies such as dual energy X-ray absorptiometry (DEXA), which truly represents the adiposity of the subject.

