#### **Study population**

Freshers admitted in MBBS course at IPGME&R and SSKM hospital. We aim to recruit 200 subjects.

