> 20% of the size of the nested cohort) will be used to validate the model. For univariate analysis non-parametric statistical test assuming unequal variance will be employed given the limited sample size. Unpaired Mann-Whitney 'U' test with Bonferroni correction for multiple testing will be used identify lipids (say, set 'A') that shows significant difference in abundance between controls and cases at a given time point. Paired Mann-Whitney test with Bonferroni correction will be used to identify lipids (say, set 'B') that shows significant change in abundance with disease onset in naive subjects. Molecules (say, set 'C') that shows similar pattern of change with time in all three groups, i.e., subjects that present PCOS at beginning, those that develop PCOS during the study and those who never develop PCOS, will be excluded from further analysis to identify putative biomarkers. Rest of the molecules that are common in both sets (A and B) and shows similar pattern of change associated with disease status will be tested as potential biomarkers related to PCOS. In addition, the correlation between lipidomic signatures and non-PCOS clinical or biochemical parameters (such as, body weight, BMI, WC, body fat, fasting glucose, insulin concentration, liver fibrosis score, etc) will be examined. Receiver operating characteristic (ROC) analysis will be performed to examine the sensitivity and specificity of these candidate biomarkers for PCOS diagnosis. In case, there are significant number of new cases of PCOS in both 2nd and 3rd year, cases up to 2nd year will be used to identify consensus lipidomic changes associated with PCOS as described above. Rest of the cases will be used to prospectively validate PCOS markers through ROC analysis. In addition, the ability of baseline abundance of such molecules to predict PCOS incidence at a later time point will be examined using ROC analysis. This would help to identify a multivariate signature that could help to predict PCOS risk in naive subjects.

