# 18. Parameters for monitoring effectiveness of the project [Please describe in detail the Key Performance Indicators (KPIs) by which the success of the project can be measure]

The effective implementation of the project can be monitored by success in manpower and patient recruitment, procurement of consumables, patient work-up, sample collection, analysis, data generation and analysis. Although it has high translational potential, the project is exploratory and basic science in nature. Therefore data presentation at national/international conferences and publication in peer-reviewed journals would also reflect effectiveness of the project.

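### The set B test is misnamed, and its evident meaning, a signed-rank test under Bonferroni, cannot be met below about 12 to 17 women with new PCOS, a number the protocol never estimates

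*Protocol*

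**What the plan says.** The univariate plan is in the Protocol, section 1.4, under Lipidomic Analysis (data mining).

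- General statement: "non-parametric statistical test assuming unequal variance will be employed given the limited sample size".
- Set A, cases against controls at one time point: "Unpaired Mann-Whitney 'U' test with Bonferroni correction for multiple testing will be used identify lipids".
- Set B: "Paired Mann-Whitney test with Bonferroni correction will be used to identify lipids", that is, lipids whose level "shows significant change in abundance with disease onset in naive subjects".
- Selection: lipids that move alike over time in all three groups (PCOS at entry, PCOS during the study, never PCOS) are dropped. The candidates are then "Rest of the molecules that are common in both sets (A and B) and shows similar pattern of change associated with disease status".

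On size, Study population says "We aim to recruit 200 subjects". The work plan has a baseline round (months 1-3) and two yearly repeats (months 13-15 and 25-27). Section 18 says that "the project is exploratory and basic science in nature".

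The protocol states no onset rate, expected number of converters, number of lipids to be tested, or significance level for the lipid tests.

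**The concern.** Set B uses only women who are free of PCOS at entry and develop it later. The sample size for that test is the number of converters, not 200. A paired rank test on few pairs has a coarse p-value with a hard lower limit, and Bonferroni over a lipidome sets a very small threshold. If the threshold lies below the limit, no effect of any size can be declared. Because a univariate candidate must be in both sets, an unreachable B empties the list whatever A shows.

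Aim 3 is how the lipid signature evolves during onset. A null result forced by the test could be reported as a finding that no such signature exists.

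A second, smaller point is that the stated tolerance of unequal variance is not a property of the test named.

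**Working it through.** **No plan figure to reproduce.** The target of 200 has no derivation, and no power or number of converters is given.

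**Inputs from the protocol.** 200 women; two yearly intervals; candidates must be in both A and B. The background section says "PCOS incidence varied widely from 6-50% among different studies". These are cross-sectional frequencies, so they bear on how many women start free of PCOS, not on the rate of onset. Two Rotterdam values in Table 1, 6% and 22.5%, give 200 × 0.94 = 188 and 200 × 0.775 = 155 women free of PCOS.

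**Assumptions.** Family-wise 0.05, two-sided; 100 to 2000 lipids (m); onset 1% to 10% per year; no dropout.

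**Step 1: floor of the signed-rank test.** The smallest exact two-sided p is 2/2^n, reached when all n women change in the same direction. The Bonferroni threshold is 0.05/m.

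| Lipids m | 0.05/m | p floor one converter short | p floor at minimum n | Minimum n |
|---|---|---|---|---|
| 100 | 0.0005 | 0.00098 (n=11) | 0.00049 | 12 |
| 500 | 0.0001 | 0.00012 (n=14) | 0.000061 | 15 |
| 2000 | 0.000025 | 0.000031 (n=16) | 0.000015 | 17 |

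A one-sided test needs one converter fewer. The normal approximation without continuity correction needs more: 16, 20 and 24.

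**Step 2: converters.** Expected number = women free of PCOS × (1 − (1 − r)²) over two intervals.

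| Onset r per year | 155 women | 188 women |
|---|---|---|
| 1% | 3.1 | 3.7 |
| 3% | 9.2 | 11.1 |
| 5% | 15.1 | 18.3 |
| 10% | 29.4 | 35.7 |

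At 1% and 3% the expected number is below the floor for every m in the range. At 5% the answer depends on m and on baseline frequency. At 10% the floor is cleared throughout. If half the women had PCOS at entry (100 free of it), the counts would be 2.0, 5.9, 9.8 and 19.0.

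**Step 3: reachable is not powered.** With 500 lipids and a paired change of 1 SD of the differences, simulated signed-rank power is 7% at n=15, 32% at n=20, 58% at n=25 and 78% at n=30.

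**Step 4: set A has no such limit.** With 12 cases and 188 controls the smallest Mann-Whitney p is about 3 × 10⁻¹⁹.

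**Step 5: an alternative for set B.** Compare converters' change with the change in never-PCOS women by Mann-Whitney. With 3 converters against 150 women the smallest p is 2/C(153,3) = 2/585,276 = 3.4 × 10⁻⁶, below 0.05/2000. With 500 lipids under Bonferroni, a 1 SD shift and 150 comparison women (assumed), simulated power against signed-rank is about 7% against 0% at 10 converters, and 25% against 7% at 15.

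**Step 6: unequal variance.** With no true shift, groups of 20 and 180 and an assumed SD ratio of 2, simulated Mann-Whitney size at nominal 5% is about 12% when the smaller group varies more and about 0.7% when the larger does. Brunner-Munzel stays near 5% in both.

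**The case against.** The strongest reply is that the plan's intent is clear. The paragraph contrasts an unpaired test for A with a paired one for B, and section 14 relies on paired analysis of the time series. A reader might infer that pairing will be ignored and precision lost, but the text does not support that. The naming fault by itself is a one-term correction. This stands.

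A reader might also infer that the candidate list is empty by construction, or empty at the likely number of converters. The documents do not support that either. They give no onset rate and no lipid count, and at 5% to 10% per year over two intervals many scenarios supply enough converters. The restriction of discovery to cases up to the second year would shrink set B, but it applies only if both follow-up years yield a significant number of new cases. With few converters it would not be triggered.

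Nor does an empty set B leave the project with no result. PLS-DA and OPLS-DA are a separate route to predictive features, and removing adducts and fragments first lowers m by an unknown amount.

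Finally, Bonferroni is valid, only strict, and no test makes very few converters informative. Both are true. What remains is a hard limit that depends on the converter count, a gate that passes it on to the candidate list, and no statement showing that the limit can be cleared. Section 14 provides extra recruitment only if cases at entry are too few, not if converters are.

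**Conclusion.** The concern holds in conditional form. The set B test is misnamed. Read as the signed-rank test evidently intended, with Bonferroni at 0.05, set B and the univariate A-and-B list must be empty below about 12 converters (100 lipids), 15 (500) or 17 (2000), and power stays modest up to about 30.

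Whether the study falls below the floor cannot be settled from the protocol. It would at onset of about 3% per year or less and would not at about 10%. Those rates, the lipid counts and the 0.05 level are assumptions.

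The unequal-variance statement is wrong for the test named. The direction of the error depends on which group varies more, and no SD ratio is documented.

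**What to change.** 1. **Set B.** Test within-woman change in log abundance in converters against change over the same interval in never-PCOS women, by Mann-Whitney or Brunner-Munzel on change scores or by a mixed model. At the least, replace the name with Wilcoxon signed-rank.
2. **Multiplicity.** Control the false discovery rate in this exploratory discovery step. This does not remove the floor if signed-rank is kept. At n=10 the floor is 0.00195, and Benjamini-Hochberg at 5% over 500 lipids needs k × 0.05/500 ≥ 0.00195, so at least 20 lipids must reach it together.
3. **Set A.** Use Brunner-Munzel, or Welch on log abundance, in line with the stated unequal variance.
4. **Planning and reporting.** State the expected converters and the number of lipids. State that an empty set B is not evidence against an onset signature when converters fall below the floor.

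The cost is wording in the analysis section; the data are already to be collected. The downside is that false discovery rate control admits some false candidates, left to the planned validation. Power stays low with few converters whichever test is used.

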#### Lipidomic Analysis:

*Lipid extraction:* 0.5 ml pre-chilled MeOH/chloroform (2:1) mixture containing internal standards will be added to the tube containing 100  $\mu$ L frozen serum sample. The mixture will be vortexed for 30 sec. 0.4 ml of ice-cold water will be added to the mixture to enable phase-separation. Sample will be mixed vigorously at room temperature for 10 minutes and centrifuged 20 mins at 14 krpm at 4°C. The lower organic layer will be collected in glass tube and dried under nitrogen flow. The sample will be reconstituted in 100 $\mu$ L internal chloroform/MeOH (1:1) containing internal standards for MS quality control. For specific lipid classes such as phospholipids and oxolipins, sample clean-up and enrichment will be performed using 96-well Oasis HLB solid-phase extraction plates.

Analysis of lipid composition: Lipids comprise of diverse class of molecules with each class consisting several distinct members that vary widely in their abundance and chemical properties. This makes analysis of lipid composition quite a challenging task. However, advances in chromatography, particularly, introduction of ultraperformance liquid chromatography coupled with high-resolution mass spectrometry has enabled significant coverage of the lipidome. In this study ultraperformance liquid chromatography (UPLC; Acquity UPLC, Waters Corp.) coupled with electrospray ionization mass spectrometry (ESIMS; Xevo G2 qTOF MS, Waters Corp) will be used for analysis of complex lipids. However, fatty acids and sterol-related compounds are not easily ionizable in ESIMS. Therefore, gas chromatography coupled with mass spectrometry (GC-MS) will be used to analyze composition of fatty acid and sterol-related compounds.

(A) UPLC-ESIMS Analysis: Lipid extract will be diluted in acetonitrile/isopropanol/water (1:2:1) and and transferred to glass sample vials for ESIMS analysis. Lipids will be separated on a reverse phase (C18) column prior to introduction to ESIMS. Samples will be run in a randomized manner with intermittent injection of pooled and authentic standard mixture samples for quality control.

Chromatograms will be aligned, deconvoluted and binned to extract features. Identification of features will be performed through analysis of MS/MS fragmentation pattern and comparison with authentic standards (whenever available).

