#### **1.6** Year wise "Activity Landmark" of the Project (1st year/ 2nd year/ 3rd year):

First year: Recruitment of JRF, train the JRF, procure consumables and software for lipiomics, and procure consumables for biochemical assays.

2nd year: Lipidomic analysis using mass spectrometry and data analysis.

3rd year: Completion of clinical data analysis and complete the project reports, manuscript for publication

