#### 1.7 Year wise deliverables output (preferably point-wise and quantified):

#### 14. Challenges & constraints:

The exact number of PCOS cases at the beginning of the study may be inadequate. In that case, additional subjects from neighbouring hospitals will be recruited. A validation cohort should also be also included in the study, particularly, in case of cross-sectional analysis. Since this longitudinal study has a nested case-control design, the new cases that are diagnosed at later time points will help to test and validate signatures identified at the beginning. Paired statistical analysis of the time series data would significantly help to weed out spurious associations. This is described in the data mining section below. However, it is desirable to have an independent cohort for validation of the results and we would like to involve other hospitals in study once a set of putative markers are identified through this study. Abundance of different lipid molecules are known differ by orders of magnitude. Particularly, phospholipids are very abundant in serum and may mask other low abundance lipids such as bioactive arachidonic acid metabolites during analysis. In order to address the issue, phospholipids will be depleted by passing samples through commercially available phospholipid-binding resin. Platform to platform variability in analysis is often a challenge in translation. To address the issue, in addition to mass spectrometry-based analysis, lipids will further be analyzed using commercially available kits.

This can help to readily validate putative PCOS biomarkers across multiple centres and translate the results into clinically relevant diagnostic assay. This study also offers the opportunity to monitor these subjects further and evaluate the prognostic potential of lipidomic signatures with respect long-term complications of PCOS.

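### Set B tests change only within women who develop PCOS, so shared change over the year can be read as onset, and rule C as written cannot be relied on to remove it

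*Protocol*

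**What the plan says.** The selection rules are in the Data mining paragraph under Lipidomic Analysis (Protocol section 1.4).

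- **Set A** is an unpaired Mann-Whitney comparison, Bonferroni-corrected, for lipids "that shows significant difference in abundance between controls and cases at a given time point".
- **Set B** is a within-woman test: "Paired Mann-Whitney test with Bonferroni correction will be used to identify lipids (say, set 'B"), meaning those "that shows significant change in abundance with disease onset in naive subjects".
- **Rule C** drops a molecule "that shows similar pattern of change with time in all three groups". The groups are women with PCOS at entry, women who develop it during the study, and women who never do.
- **Candidates** must be in both A and B, survive rule C, and change in a way consistent with disease status.

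Section 14 (Challenges & constraints) says what pairing is expected to do: "Paired statistical analysis of the time series data would significantly help to weed out spurious associations".

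On assay order, the UPLC-ESIMS paragraph says: "Samples will be run in a randomized manner with intermittent injection of pooled and authentic standard mixture samples for quality control". The GC-MS paragraph has no such sentence. The work plan draws serum in months 1–3, 13–15 and 25–27 and schedules lipidomics for months 3–34. Section 1.6 gives as the second-year landmark "year: Lipidomic analysis using mass spectrometry and data analysis".

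**The concern.** All participants enter as first-year medical students and are re-examined yearly. A before/after test in converters alone estimates onset plus everything else that moved in that interval. Pairing removes stable differences between women. It does not remove effects of time, so the reassurance in section 14 does not cover this.

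Rule C is the only stated safeguard aimed at time effects, and its form is weak. It requires the pattern to be alike in all three groups. Drift shared by converters and never-PCOS women is therefore kept whenever women with PCOS at entry behave differently. No measure of similarity is given, and the result depends heavily on which one is used.

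Aim 3 is to characterise how the lipid signature evolves during onset, and set B is its main univariate route. A lipid that already differed before onset, and then moved with time in everyone, would be reported as changing because of onset. The study exists to draw that distinction, and section 1.1.2 criticises earlier cross-sectional work for not accounting for BMI.

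**Working it through.** There is no figure in the plan to reproduce. The only stated size is the target: "We aim to recruit 200 subjects". No alpha, number of lipids, expected number of converters or variance is given.

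**Assumed inputs.** Alpha 0.05, 300 lipids, 15 to 30 converters, 20 women with PCOS at entry (45 as an alternative), and the rest of 200 never-PCOS. Every woman drifts by 0.5 or 1 SD of within-woman change, and there is no onset effect. The stable case-control difference is 0 or 1 SD, in the same direction as the drift. There were 1,500 simulated runs per scenario, so a rate near 38% has a standard error of √(0.38 × 0.62 / 1500) ≈ 1.3 percentage points.

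**Step 1: when can set B contain anything?** The per-lipid threshold is 0.05/300 = 0.000167. The smallest two-sided signed-rank p-value with n pairs is 2/2^n. For n = 13 it is 2/8192 = 0.000244, too large. For n = 14 it is 2/16384 = 0.000122, small enough. With 300 lipids, set B is empty below 14 converters. For 100, 500 and 1,000 lipids the minimum is 12, 15 and 16.

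**Step 2: how often does shared drift alone put a lipid in set B?**

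| Converters | 1 SD drift, paired test |
|---|---|
| 15 | about 12% |
| 20 | 36–39% |
| 30 | 82–84% |

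At 0.5 SD drift the range is about 1–8%. A Mann-Whitney comparison of converters' changes with never-PCOS women's changes flagged such a lipid in 0 to 0.07% of runs.

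**Step 3: what does rule C leave in set B?** With 20 converters, 20 women with PCOS at entry, and 1 SD drift shared by all:

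| Reading of similar pattern | Left in set B |
|---|---|
| Bonferroni-significant in all three groups | 24–25% |
| No group difference in change (Kruskal-Wallis p ≥ 0.05) | 2.3–2.7% |
| p < 0.05 in all three groups | 0.4–0.5% |
| Same direction in all three groups | 0% |

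The first row falls to about 0.5% with 45 women with PCOS at entry, so that reading depends on the power of the smallest group. If women with PCOS at entry do not share the drift, 17–18% (same direction) to 37–38% (Bonferroni) stay in set B.

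**Step 4: what passes set A as well?** With no case-control difference and drift shared by all, 0% become candidates. With a stable 1 SD difference, 20 women with PCOS at entry and the Bonferroni reading of rule C, about 20–24% (20 converters) or 48–49% (30 converters) become candidates. If women with PCOS at entry do not share the drift (20 converters), 1–4% do.

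**The case against.** The strongest reply is that set B is only half of the selection. Set A compares cases with controls at one time point, where drift common to all women cancels. A reader might infer that ageing or run-drift lipids would pass straight into the biomarker list. The documents do not support that: a lipid that drifts equally in all women and does not differ between cases and controls fails set A.

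A reader might also infer that rule C achieves nothing. That is too strong. It is written against shared time effects, and when all groups share the drift, three of the four readings remove nearly all such lipids. A test or threshold for similarity could also be left to an analysis plan. What remains is the requirement, fixed in the Protocol, that all three groups look alike.

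Error rates worked out at an uncorrected 5% level would exaggerate the problem, because the plan uses Bonferroni correction. With 8 converters the smallest possible p-value is 2/2^8 = 0.0078, so set B would be empty with 7 or more lipids.

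Assay by collection wave is a risk the timetable permits. It is not an established fact. Randomised UPLC-MS runs with pooled quality-control samples are planned, aliquots are stored at −80 °C, and the assay window runs to month 34. The text leaves open whether randomisation spans the yearly collections, and it gives no run order for GC-MS.

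Finally, the Protocol calls the project exploratory. It plans ROC checks in later cases if numbers allow, and independent cohorts afterwards. Its test of baseline abundance as a predictor is not inflated by within-woman drift. This limits the harm to clinical claims but does not correct the label of onset change.

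**Conclusion.** The point holds in a limited form. Set B has no concurrent comparator, although the cohort already contains the right one. Pairing does not deal with time effects, and rule C cannot be relied on to do so. The set A requirement confines the damage to lipids with a stable PCOS or adiposity difference that also drift with time. These can be reported as onset changes, which affects Aim 3.

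The size depends on inputs the Protocol does not give. Under the assumptions above, up to about half of such lipids become candidates (30 converters, 1 SD drift, the least favourable reading of rule C). Other readings leave far fewer when all groups share the drift. The high figures also assume that drift runs in the same direction as the case-control difference, since the plan asks for a pattern consistent with disease status. The absence of a comparator in the set B test rests on none of these assumptions.

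**What to change.** Define set B as lipids whose change in log abundance over the onset interval differs between converters and never-PCOS women over the same interval. Use a Mann-Whitney test on change scores or a group-by-time contrast, Bonferroni-corrected. This replaces both the paired test and rule C. Amend the sentence in section 14 so that protection against time effects is credited to this comparison and not to pairing.

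State, for both UPLC-MS and GC-MS, that converters and never-PCOS women are randomised together within every run. Where stored aliquots allow, run a woman's serial samples in the same batch. Deferring all longitudinal assays until after month 27 is not required: with both groups mixed in each run, shared run drift cancels in the comparison of changes.

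The cost is analysis wording, a little batch planning, and somewhat lower power than the paired test. No extra women, visits or serum are needed.

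### The set C deletion rule leaves similarity of change undefined. Judged by direction alone, it deletes lipids that drift in all women and change further at PCOS onset

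*Protocol*

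**What the plan says.** The Data mining text under Lipidomic Analysis (Protocol section 1.4) builds the univariate biomarker list in three steps.

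- **Set A**: an unpaired Mann-Whitney test with Bonferroni correction finds each lipid that "shows significant difference in abundance between controls and cases at a given time point".
- **Set B**: a paired test, also Bonferroni-corrected, finds each lipid that "shows significant change in abundance with disease onset in naive subjects". Only the converters enter this test.
- **Set C**: a molecule that "shows similar pattern of change with time in all three groups" "will be excluded from further analysis to identify putative biomarkers".

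What goes forward is described as "Rest of the molecules that are common in both sets (A and B) and shows similar pattern of change associated with disease status". The prediction analysis works on the same survivors: "the ability of baseline abundance of such molecules to predict PCOS incidence at a later time point will be examined using ROC analysis". A lipid removed by set C therefore leaves the univariate route to both the diagnostic and the predictive ROC analyses.

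No direction, magnitude, test or threshold defines a similar pattern. No test compares the change in converters with the change in never-PCOS women.

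**The concern.** A time trend shared by all women does not show that a lipid is unrelated to PCOS. The lipid can rise in everyone and rise further in those who convert. Whether set C deletes it depends on what is meant by similar.

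Shared trends are plausible here. The subjects are first-year medical students re-examined yearly, with sampling at months 1-3, 13-15 and 25-27 and laboratory work spread over months 3-34 (Work plan). Ageing and student life can move all three groups together.

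At stake is the candidate list. If the rule is applied by direction, an empty or short list could come from the filter rather than from the biology, and the report would not show which.

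**Working it through.** **Inputs from the Protocol.** Planned size: "We aim to recruit 200 subjects". Frequency at entry: "PCOS incidence varied widely from 6-50% among different studies", so 12 to 100 of 200 women. Sets A, B and C are as described above. The Protocol gives no effect size, drift, within-woman correlation, converter number, lipid count or deletion rate, so there is no figure of its own to reproduce.

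**Assumed inputs.** Unit SD at each visit; within-woman correlation 0.6; 25 women with PCOS at entry (other splits where stated); 15-30 converters; onset jump 0.8-1.5 SD; shared drift 0.5 SD; 100 or 300 lipids. SD of a one-year change = sqrt(2 x (1 - 0.6)) = 0.894.

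**Step 1: how often does drift alone put the comparison groups in set C?** Women with PCOS at entry do not have an onset during the study, so only the drift moves them. With 25 of them the standard error of the mean change is 0.894/sqrt(25) = 0.179, and 0.5/0.179 = 2.80.

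- Same sign: the chance that their mean moves with the drift is Phi(2.80) = 0.997.
- Significant at 5%: Phi(2.80 - 1.96) = Phi(0.84), about 0.80.

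The never-PCOS group is large and almost always shows the drift; converters show drift plus jump. So a direction rule captures a true onset lipid nearly always (same sign) or about three times in four (each group significant; the simulations give 74-78%).

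**Step 2: count only lipids that would otherwise qualify.** The relevant loss is passing A and B and then falling to C.

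| Setting (0.5 SD same-direction drift) | Result |
|---|---|
| 25 at entry, 15 converters, 0.8 SD, 100 lipids | 58% pass A and B; about 46% of all runs pass and are then deleted (each group significant) |
| Same, 300 lipids | 37% pass; 30% pass and are then deleted |
| 15-30 converters, 0.8-1.5 SD, 100 lipids, each group significant | 45-77% pass and are then deleted |
| Same range, same sign | 57-99% |
| Same range, similar = no group difference in change | at most 4%; up to 7% for a 0.5 SD jump |

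The lower ends follow from the pass rate: 0.58 x 0.77 = 0.45 and 0.58 x 0.99 = 0.57.

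A separate simulation with 45 at entry, 20 converters, 135 never-PCOS, a 1.5 SD jump and 300 lipids agrees. The lipid is in A and B in 99.9% of runs. It is kept after C in 0.1% (same sign), 6.7% (each group significant) or 99.9% (size counts). With 12 at entry, 20 converters and 168 never-PCOS the figures are 5.5%, 60.6% and 99.9%. On the significance reading, then, a lipid's fate depends on how many women had PCOS at entry.

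**Step 3: when does set C not matter?**

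- Drift of 0.5 SD opposite to the onset effect: deletion in 0% of runs.
- No drift: deletion is 0-3% on the significance reading. The same-sign reading still deletes about a quarter by chance (1/2 x 1/2; 24% simulated).
- 10 converters: the smallest two-sided exact signed-rank p is 2/2^10 = 0.00195, above 0.05/100 = 0.0005. Set B can pass nothing, so C costs nothing.
- A constant level difference of 1 SD without drift: in A in 99.6% of runs but in B in 0%. The requirement to be in both sets loses it, not C.

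**Step 4: the direct contrast.** Converters' change minus never-PCOS change cancels shared drift. It detects 1.2-1.5 SD onset lipids in 86-100% of runs with 15 or more converters, whatever the drift, and flags a drift-only lipid in about 0%. With opposite drift, a 1.5 SD jump and the 12/20/168 split, set B passes 51% where the contrast detects 99.7%.

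Smaller jumps remain hard. For 0.8 SD, 15 converters and 160 never-PCOS, the standard error is 0.894 x sqrt(1/15 + 1/160) = 0.242, and 0.8/0.242 = 3.31 against a critical value of 3.48, so power is about 43%. With 30 and 145 it is about 84%. These are normal approximations; a rank test would do worse.

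**The case against.** The best defence is that set C is a sensible negative control. Set B is an uncontrolled before-after test in converters: with a 1 SD drift and no link to disease it flags a lipid in 53% of runs (20 converters) to 94% (30 converters). Set C uses never-PCOS women to remove such lipids, and one that changes equally in all groups has no onset-specific change. This stands, so the rule's purpose should be kept. The defence is weakened only in that set A already rejects pure drift.

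Second, a pattern can include size. A lipid that moves further in converters is then outside set C, and little is lost. This also stands. A reader might infer that the rule is bound to discard real markers; the Protocol does not support that, because it does not impose the direction reading. It does not exclude that reading either.

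Third, a reader might count every true lipid that C would delete, including those that A and B would already have dropped. For a 0.5 SD jump on the size reading that gives 57-68%, whereas the loss among lipids that passed A and B is at most 7%. The larger figure overstates the cost of C.

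Fourth, a reader might blame C for losing lipids that differ by a constant amount. Without drift they fail set B regardless.

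Last, internal standards, randomised run order and pooled quality-control injections address assay drift. They do not remove real ageing or lifestyle change, and the Protocol does not say whether one woman's yearly samples share a batch.

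**Conclusion.** The point holds in a conditional form. The Protocol fixes a hard deletion step on an undefined term and specifies no contrast of change between converters and never-PCOS women. Under a direction reading the loss of otherwise qualifying onset lipids is large (roughly 45-99% of runs); under a size reading it is small (about 0-7%). The first range needs a shared drift in the same direction as the onset effect and about 15 or more converters. Drift, effect sizes, correlation, converter numbers and lipid count are all assumed.

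A definition alone would limit the damage. A direct contrast is better, because it does the work of B and C together and also recovers onset lipids masked by opposite drift. This should be settled before the lipidomic data are analysed.

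**What to change.** Replace set B and set C together with one contrast per lipid: change in converters against change in never-PCOS women over the same visits. Use the group-by-visit term of a model or a rank test on change scores, with the multiplicity correction retained. Do not remove set C without this replacement, since set B would then have no concurrent control.

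Assess constant level differences separately, by comparing baseline levels of future converters with those of never-PCOS women, and let those lipids enter the baseline-prediction ROC analysis without having to pass the change test.

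The cost is a few sentences in the data-mining text and slightly more analysis, with no extra women or samples. One downside: some lipids that set B would have passed only with the help of same-direction drift will no longer qualify. At 15 converters and a 0.8 SD jump, such drift raises the set B pass rate from 18% to 73% (100 lipids).
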